8.1 Discontinuation of Study Intervention

Discontinuation from the AKL-T01 intervention does not mean discontinuation from the study, and we will attempt to complete remaining study procedures as indicated by the study protocol. If a clinically significant finding is identified (including, but not limited to changes from baseline) after enrollment, the investigator or qualified designee will determine if any change in participant management is needed.

The data to be collected at the time of study intervention discontinuation will include the collection of the post-intervention assessment data, including all cognitive tasks, functional assessments, and mood symptom scales.

8.2 Participant Discontinuation/Withdrawal from the Study

Participants are free to withdraw from participation in the study at any time upon request. An investigator may discontinue or withdraw a participant from the study for the following reasons:

- Significant study intervention non-compliance
- If any clinical adverse event (AE), laboratory abnormality, or other medical condition or situation occurs such that continued participation in the study would not be in the best interest of the participant.
- Participant lost to follow-up after several attempts to contact subject to schedule study visit.

The reason for participant discontinuation or withdrawal from the study will be recorded in the case report form (CRF). Subjects who sign the informed consent form and are randomized but do not receive the study intervention may be replaced. Subjects who sign the informed consent form, and are randomized and receive the study intervention, and subsequently withdraw, or are withdrawn or discontinued from the study, will not be replaced.

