For participants without access to technology that would allow them to consent electronically, the participant and researcher will review the consent form over the phone. A copy of the consent form will be mailed or emailed to the participant in advance so that it can be viewed by the participant during the phone call. They will return the signed consent form in a stamped, self-addressed envelope provided by the researcher. These participants will then be mailed a copy of their signed consent form for their records.

To screen prospective participants, we will conduct an initial screening via a secure HIPAA-compliant videoconferencing platform (Zoom). Participants will be queried for inclusion and exclusion criteria. Participants will be administered via Zoom the Oral Trail Making Test, Stroop Test, and the Frontal Systems Behavior Rating Scale (FrSBe). Participants will be eligible for enrollment if they score <1 standard deviation below their age-normed peers on at least one of these three screening tests.

Participants will be randomized into the intervention arm or a waitlist control arm, with an option for the control participants to receive the AKL-T01 intervention at the conclusion of the initial 6-week waitlist period.

All participants (intervention & waitlist control arm): Full assessment visits will take place pre-intervention (baseline) and post-intervention (week 6). During the 6-week intervention period, shorter intermediate assessment visits will take place at weeks 2 and 4. Participants in the waitlist control arm will continue any ongoing self- or provider-based cognitive intervention (or no intervention) during the initial 6-week waitlist period.

Participants in the intervention arm & participants in the control arm who decline the intervention: A full assessment session at will take place at week 10 (4 weeks post-intervention) for longitudinal follow-up.

Participants in the control arm who begin the intervention at the conclusion of the waitlist period: The week 6 assessment visit will also serve as the baseline for the beginning of the intervention. Intermediate assessment visits will take place at weeks 8 and 10, a full post-intervention assessment visit will take place at week 12, and a follow-up assessment visit will take place at week 16 (4 weeks post-intervention).

See Section 6.1 for the complete Schedule of Assessments.

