7.9 Duration of Therapy and Criteria for Removal from Study

In the absence of intervention delays due to adverse event(s), intervention may continue until one of the following criteria applies:

- Intercurrent illness that prevents further administration of the intervention,
- Unacceptable adverse event(s),
- Subject decides to withdraw from the study, or
- General or specific changes in the subject's condition render the subject unacceptable for further intervention in the judgment of the investigator.
- The investigators of this study may stop the study or remove participants from the study at any time should they judge that it is in the participants' best interest to do so or if they do not comply with the study plan.

For device/interventional studies -

Study Termination Guidelines: A subject's follow-up in the study will end after one of the following applies:

- Subject's voluntary withdrawal
- Subject lost to follow-up
- Completion of all scheduled study follow-up appointments

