7.12 Study Intervention/Follow-up Compliance

Adherence to video game play for the participants in the AKL-T01 intervention arm will be monitored by a member of the research team using the intervention dashboard, which provides the researchers with information about duration and frequency of gameplay, progression through game levels, etc. Participants who are not playing for the required duration of 25 minutes a day for at least 5 days a week will work with their care manager during a weekly check-in visit to make a plan for game play (e.g., playing at a specific time each day, setting reminders to play).

Participants will be considered lost to follow up and no longer participating in the study when they do not respond to attempts at communication with the researcher for two weeks and miss an assessment visit during that window.

8. Study Intervention Discontinuation and Participant Discontinuation/Withdrawal

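### Section 8.2 permits withdrawal from the study for not complying with the game, a ground that before week 6 only AKL-T01 participants can meet, so primary outcomes could be lost selectively in one arm

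*Combined protocol and SAP*

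**What the plan says.** Section 8.2 separates nothing between leaving the game and leaving the trial. It reads "An investigator may discontinue or withdraw a participant from the study for the following reasons" and opens its list with "Significant study intervention non-compliance". What counts as significant is not defined, and no week-6 assessment is required of someone withdrawn this way.

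Section 8.1 takes the opposite line: "Discontinuation from the AKL-T01 intervention does not mean discontinuation from the study". The same sentence commits the team to attempt the study procedures that remain. It adds: "The data to be collected at the time of study intervention discontinuation will include the collection of the post-intervention assessment data".

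Section 7.9 contains two lists. The last item of the first list allows removal from the study in the participant's best interest "or if they do not comply with the study plan". The second, the Study Termination Guidelines, says that a subject's "follow-up in the study will end after one of the following applies" and names voluntary withdrawal, loss to follow-up and completion of visits. Non-compliance is not among them.

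Section 7.12 provides for gameplay monitoring in the AKL-T01 arm. Those who play too little "will work with their care manager during a weekly check-in visit to make a plan for game play". It does not say what follows if that plan fails.

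For the control arm, section 3.1 says: "Participants in the waitlist control arm will continue any ongoing self- or provider-based cognitive intervention (or no intervention) during the initial 6-week waitlist period".

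Section 12.1 promises an intent-to-treat analysis that keeps the outcomes of people who did not finish the intervention. Sections 12.1 and 12.4.1 compare change scores by ANOVA and give no missing-data method. Sections 10 and 12.2 describe a linear mixed model instead.

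**The concern.** The primary endpoint is change in Digit Symbol Matching from baseline to week 6. A rule that ends study participation because of behaviour after randomisation can remove that endpoint for the people to whom it is applied. Here the behaviour is use of the game, which before week 6 exists in one arm only. The decision also cannot be made without knowing the allocation.

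Any resulting loss is therefore one-sided and may be related to outcome. If low players would have improved less than the rest, losing them flatters AKL-T01. If they would have improved more, for example because they recovered sooner and lost interest, losing them works against it. An intent-to-treat label cannot repair this, because it can only include outcomes that were collected.

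**Working it through.** **Step 1: which arm each clause reaches before week 6.**

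| Clause | AKL-T01 | Waitlist |
|---|---|---|
| 8.2, non-compliance with the study intervention | yes | no, there is no study intervention yet (3.1) |
| 7.9 first list, non-compliance with the study plan | yes | yes, through check-ins and assessments |
| 8.1, stopping the game | stays in the study | not applicable |

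Only the 8.2 ground is confined to one arm.

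**Step 2: complete-case bias.** The documents give 50 participants per arm (12.2) and alpha 0.05. They give no withdrawal rate. Assume:
- a share p of the AKL-T01 arm is withdrawn under 8.2 and would otherwise have attended week 6;
- their mean change would have been delta change-score SDs below that of those retained;
- there is no true effect, and the SD is 1 in both arms.

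If the retained mean is m, the full-arm mean is (1 − p)m + p(m − delta) = m − p × delta. The complete-case comparison is therefore shifted by p × delta.

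**Step 3: type I error.** For a two-sided t-test at 0.05, the noncentrality is bias × sqrt(n1 × n2/(n1 + n2)). The multiplier is sqrt(45 × 50/95) = 4.867 at p = 10% and sqrt(40 × 50/90) = 4.714 at p = 20%.

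| delta | Bias, p = 10% | Type I error | Bias, p = 20% | Type I error |
|---|---|---|---|---|
| 0 | 0 | 5.0% | 0 | 5.0% |
| 0.25 | 0.025 SD | 5.2% | 0.05 SD | 5.6% |
| 0.5 | 0.05 SD | 5.7% | 0.10 SD | 7.5% |
| 1.0 | 0.10 SD | 7.7% | 0.20 SD | 15.4% |

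A negative delta gives the same sizes with the bias reversed.

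**Step 4: what the mixed model recovers.** Take a random-intercept model, a deficit that builds linearly over weeks 0 to 6, and no scores after withdrawal. Let S be the sum of squared deviations of the observed weeks from their mean. S is 20 for weeks 0, 2, 4 and 6; 8 for weeks 0, 2 and 4; 2 for weeks 0 and 2; and 0 for week 0 alone. As the intraclass correlation approaches 1, bias/delta = p − pS/(20(1 − p) + pS). At p = 20%:
- withdrawal after week 2: 0.2 − 0.4/16.4 = 0.1756, a reduction of 12%;
- withdrawal after week 4: 0.2 − 1.6/17.6 = 0.1091, a reduction of 45%;
- no score after baseline: no reduction.

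These are the most favourable values. Generalised least squares for the same model gives reductions of about 10% and 43% at an intraclass correlation of 0.8, and about 5% and 38% at 0.5. The documents state no intraclass correlation, so the result is a range: 5–12% after week 2 and 38–45% after week 4.

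The bias is not expressed as a share of the planned effect of about 0.4, because section 12.2 does not say on which SD that figure is scaled.

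**The case against.** The best defence is that the protocol already protects these outcomes. Section 8.1 keeps people who stop playing in the study and commits the team to attempt the remaining visits, so week 6 should still be sought. Section 7.12 answers low play with a care-manager plan, and 8.2 is permissive. All of that stands, and it means the loss is conditional. It does not close the 8.2 route, which remains open to an investigator and carries no duty to obtain week 6.

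The illustration also charges the whole of p × delta to this clause. Some persistent non-players would leave or become unreachable anyway, and no wording would recover their data. The 15.4% needs a fifth of the arm withdrawn and a full-SD gap; at 0.25 SD the inflation is slight.

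A reader might infer more than the documents support in four places:
- **That 7.9 flatly forbids withdrawal for non-compliance.** The termination list does not claim to be exhaustive, and it also omits the adverse-event withdrawal that 8.2 allows. It sits badly with 8.2 without clearly contradicting it.
- **That every non-compliance clause is one-sided.** The study-plan clause in 7.9 can reach either arm.
- **That 3.4 restricts the analysis to people who completed the game.** Read literally, its completion definition would leave no waitlist completers at week 6, so it cannot be an analysis-set rule. Section 12.1 refers to all randomised participants.
- **That the early battery in 8.1 is meant to replace week 6.** The commitment to remaining procedures points the other way, although the text would be safer if it said so.

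**Conclusion.** The point holds as a conflict between 8.2 and 8.1 that undermines intent-to-treat. An undefined, discretionary ground, available in one arm only before the primary endpoint and applied with knowledge of the arm, can end collection of the primary outcome. The conflict rests on the text alone.

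The size is conditional. Over the assumed range, the complete-case type I error runs from 5.2% to 15.4%, in a direction set by the sign of delta, and the mixed model removes less than half of the bias. The documents do not show that such withdrawals will occur, how many there would be, or that they would favour AKL-T01. This should be corrected before the trial relies on it, but it is not evidence that the result will be biased.

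**What to change.** - In 8.2, delete non-compliance with the intervention as a ground for withdrawal from the study.
- In 7.9, limit the non-compliance clause to stopping the game under 8.1.
- State that all randomised participants in both arms stay on the week 2, 4 and 6 assessment schedule whatever their gameplay, unless they withdraw consent, are lost to follow-up or assessment is unsafe.
- In 8.1, state that a battery collected early does not replace the week-6 visit.
- Optionally, in 3.4, define completion for the primary objective as the week-6 assessment, so that it fits both arms.

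The dose wording and the no-replacement rule can stay as they are. The cost is wording only: the remote visits are already in the schedule (6.1) and the compensation table (4.6), and no extra participants, visits or measures are needed. The change does not deal with outcomes missing for other reasons.

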8.3 Lost to Follow Up

A participant will be considered lost to follow-up if they do not complete a scheduled visit within two weeks of the assessment window and is unable to be contacted by the study site staff.

The following actions must be taken if a participant does not complete a required study visit:

- The site will attempt to contact the participant and reschedule the missed visit for two weeks and counsel the participant on the importance of maintaining the assigned visit schedule and ascertain if the participant wishes to and/or should continue in the study.
- Before a participant is deemed lost to follow-up, the investigator or designee will make every effort to regain contact with the participant (where possible, 3 telephone calls and, if necessary, a certified letter to the participant's last known mailing address or local equivalent methods). These contact attempts should be documented in the participant's medical record or study file.
- Should the participant continue to be unreachable, he or she will be considered to have withdrawn from the study with a primary reason of lost to follow-up.

9. Correlative/Special Studies

Not applicable.

9.1 Laboratory Correlative Studies

Not applicable.

9.1.1 Title – Laboratory Correlative Study #1

9.1.1.1 Collection of Specimen(s)

9.1.1.2 Handling of Specimen(s)

9.1.1.3 Shipping of Specimen(s) (if multicenter)

9.1.1.4 Site(s) Performing Correlative Study (if multicenter)

9.2 Special Studies

Not applicable.

9.2.1 Title – Special Correlative Study #1

9.2.1.1 Assessment

9.2.1.2 Method of Assessment

9.2.1.3 Timing of Assessment

10. Measurement of Effect

Calculated for primary and secondary outcome measures, comparing the active intervention (AKL-T01; week 0 to week 6 for intervention arm) to the waitlist control (week 0 to week 6) using standard inferential statistical techniques and calculation of effect sizes. Formally, for primary and secondary outcomes, we will apply linear mixed effects models with fixed effects for treatment group as the between-subjects factor, time (week number) as the within-subjects factor, and group-by-time interaction. A random intercept will be included. Effect size will be reported in terms of group-by-time interaction (i.e., difference in slope of change between

groups). Despite the protection afforded by randomization, should potential confounding variables be identified from among baseline sociodemographic and clinical features, secondary analyses will incorporate fixed terms for those putative confounders in linear models.

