Study Design:	This study is a randomized clinical trial designed to compare efficacy of the AKL-T01 intervention relative to a waitlist control in patients who were infected with COVID-19. Participants will be selected for the presence of cognitive dysfunction prior to enrollment in the trial and will be randomized to the intervention arm or the waitlist control arm. They will complete an assessment battery designed to assess cognition, functional outcomes, and

mood symptoms at pre-intervention (at study entry) and post-intervention (following 6 weeks of AKL-T01 or waitlist). The assessment battery will also be administered bi-weekly during the intervention period (i.e., at weeks 2 and 4), and 4 weeks after the end of the intervention period for longitudinal follow-up. We will use a waitlist design; at the end of the intervention period, participants in the control group will have the option to receive the 6-week AKL-T01 intervention. Note that study visits will take place remotely and devices for intervention administration will be mailed to participants.

**Description of Sites/
Facilities Enrolling
Participants:**

Participants will be enrolled through facilities of the Manhattan Campuses of NewYork-Presbyterian Hospital (NYP)/Weill Cornell Medicine (WCM), as well as the NewYork-Presbyterian Westchester Behavioral Health Center.

Study Duration: The study duration will be two years, including 12 months to recruit, collect data, and conduct data analysis and one additional year to publish results of the study.

Participant Duration: Participants in the AKL-T01 intervention group will be enrolled in this study for approximately 10 weeks, comprised of the 6-week intervention period and week 10 longitudinal follow-up (4 weeks after completing the intervention). Participants in the waitlist control group who choose to begin the intervention after the initial 6-week period will be enrolled for 16 weeks, comprised of the 6-week waitlist period, the 6-week intervention, and week 16 longitudinal follow-up (4 weeks after completing the intervention).

Study Agent/Device Name

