6.1.2 Treatment Phase

6.1.2.1 Week 0 (Baseline/Pre-Intervention), Week 6 (Post-Intervention), Week 12 (Post-Intervention; waitlist control participants only)

The pre- and post-intervention visits will take place at the beginning and the end of the intervention period. Participants in both arms will meet remotely with a member of the research team via a HIPAA-compliant video conferencing platform (Zoom). The full battery of cognitive tasks (~35 minutes), functional assessments (~30 minutes), and mood symptom scales (~10 minutes) will be conducted at the baseline visit. Participants in the AKL-T01 intervention arm will be trained in procedures for gameplay during this visit. (Note that the week 6 assessment session will also serve as the baseline assessment for control participants who begin the intervention following the waitlist period.)

The pre- and post-intervention assessment visits will include the following study procedures:

- **Cognitive Tasks:**
- Digit Symbol Matching

- Multiple Object Tracking
- Digit Span Backwards
- Simple RT
- Choice RT
- Letter/Number Switch
- Gradual CPT
- Visual Paired Associates
- **Functional Assessments:**
- NeuroQOL
- WHODAS (36-item)
- Modified Fatigue Impact Scale
- **Mood Symptom Scales:**
- PHQ-9
- GADS-7

6.1.2.2 Weeks 2 & 4 (\pm 2 days; *all participants*) & Weeks 8 & 10 (\pm 2 days; *waitlist control participants only*)

The intermediate assessment visits at weeks 2 & 4 (and weeks 8 & 10 for waitlist control participants) will include a shorter battery of cognitive tasks (~25 minutes) and functional assessments (~10 minutes) measuring the primary and secondary endpoints, as well as the PHQ-9 (~5 minutes) for monitoring of mood symptoms.

The intermediate assessment visits will include the following study procedures:

- **Cognitive Tasks:**
- Digit Symbol Matching
- Multiple Object Tracking
- Digit Span Backwards
- Simple RT
- Choice RT
- Letter/Number Switch
- Gradual CPT
- **Functional Assessments:**
- NeuroQOL
- WHODAS (12-item)
- **Mood Symptom Scales:**
- PHQ-9

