12.2 Sample Size/Accrual Rate

Our target sample size will be 100 COVID-19 survivors. 50 participants will be randomized to the AKL-T01 intervention arm and 50 participants will be randomized to a waitlist control arm.

Our total enrollment to meet our target sample size of 100 participants will be 125. Based on previous research conducted at our institution, we anticipate ~20% of individuals will decide not to participate after meeting eligibility criteria.

As primary analysis will utilize linear mixed models (as implemented in lme4) to examine slope of symptom change, we utilized the simr package in R (4.0) to estimate power for the specified model assuming 50 participants per study arm in 100 simulated data sets. For standardized beta coefficient corresponding to Cohen's d of ~0.4, power exceeds 88% (95% confidence interval 80.0-93.6%) for the base case, and exceeds 80% under a range of conservative assumptions, with alpha=0.05 for the primary hypothesis test.

We expect enrollment to last approximately 12 months, yielding an accrual rate of ~10 participants per month.

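### If weeks 2 and 4 enter the random-intercept slope model, and people's slopes differ or correlation falls with time, the test exceeds its stated 5% error rate

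*Combined protocol and SAP*

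**What the plan says.** Section 10 (Measurement of Effect) applies one linear mixed model to the primary and secondary outcomes. Its fixed effects are arm, "time (week number) as the within-subjects factor", and their interaction. On random terms it says only "A random intercept will be included". On the effect it says "Effect size will be reported in terms of group-by-time interaction (i.e., difference in slope of change between" the groups. No random slope, residual correlation structure or robust standard error is mentioned anywhere in the document.

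Section 12.2 introduces the power calculation with "As primary analysis will utilize linear mixed models (as implemented in lme4) to examine slope of symptom change" and gives the power "with alpha=0.05 for the primary hypothesis test". Sections 12.1 and 12.4.1 instead compare baseline-to-week-6 change scores between arms by ANOVA.

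On visits, Section 3.1 states that "shorter intermediate assessment visits will take place at weeks 2 and 4", and Section 6.1.2.2 describes their content as "measuring the primary and secondary endpoints". Sections 6.1 and 6.1.2 place Digit Symbol Matching, NeuroQOL and the six other secondary cognitive tasks at weeks 0, 2, 4 and 6. Section 10 does not list the visits that enter the model.

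**The concern.** With four visits, a random intercept alone implies that everyone in an arm shares one true slope and that any two visits are equally correlated. The quantity under test is itself a slope. If people change at different rates, that variation belongs in the standard error of the arm difference. The model sees it only as ordinary within-person residual, averages it over three within-person degrees of freedom, and so counts about a third of it. Correlation that falls with time between visits has a similar effect. The confidence interval is then too narrow and the test rejects too often.

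Differing rates of change are plausible here. Section 2.2 describes a game that adapts to each player's ability, and Section 7.12 foresees participants who play less than required. The document does not quantify this variation. At stake is whether the primary test holds its stated alpha.

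**Working it through.** **The plan's own figure.** Section 12.2 gives 88% power with a 95% interval of 80.0–93.6% from 100 simulated data sets. That is the exact binomial interval for 88 of 100. The 88% itself can be neither confirmed nor refuted, because the ICC, the visits and any slope variance are not given. A plain two-sample comparison with d = 0.4 and 50 per arm has 51.6% power (two-sided). The random-intercept model reaches 88% if the ICC is about 0.774 with four visits, or about 0.796 with two.

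**Inputs.** From the plan: 50 per arm, 1:1, alpha 0.05 (taken as two-sided), visits at weeks 0, 2, 4 and 6. Assumed: baseline SD of 1, the ICC, the SD of true six-week change, and the correlation patterns.

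**Formula.** The centred visit times are −3, −1, 1 and 3 weeks, with sum of squares 20. Write s² for residual variance and b² for the variance of true weekly slopes.
- True variance of one person's fitted slope: s²/20 + b².
- Variance the random-intercept model assigns: average within-person variance / 20 = s²/20 + b²/3.
- With f = b²/(s²/20 + b²), the true-slope share of fitted-slope variance, assigned/true = 1 − 2f/3.
- Type I error = 2 × P(Z > 1.96 × √(1 − 2f/3)).

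**Example.** ICC 0.7 and SD of true change 0.5: s²/20 = 0.3/20 = 0.0150; b² = (0.5/6)² = 0.00694; f = 0.00694/0.02194 = 32%. The standard error ratio is √0.789 = 0.89, and type I error is 2 × P(Z > 1.74) = 8.2%.

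| ICC | SD of true change | f | Stated SE / true SE | Type I error |
|---|---|---|---|---|
| 0.5 | 0.3 | 9% | 0.97 | 5.7% |
| 0.7 | 0.3 | 14% | 0.95 | 6.2% |
| 0.8 | 0.3 | 20% | 0.93 | 6.8% |
| 0.5 | 0.5 | 22% | 0.92 | 7.0% |
| 0.7 | 0.5 | 32% | 0.89 | 8.2% |
| 0.8 | 0.5 | 41% | 0.85 | 9.5% |

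At SD 0.7 the range is 8.6–12.4%. Without choosing an ICC or SD, type I error is 5.8% at f = 10%, 6.8% at 20%, 8.0% at 30% and 9.3% at 40%.

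**Decaying correlation, no random slopes.** Take 20% visit-level noise and correlation 0.8 per two weeks in the rest. True slope variance = 0.2/20 + 0.8 × 11.104/400 = 0.0322. Assigned variance = (1 − 0.8 × 0.699)/20 = 0.0221. The true/assigned ratio is 1.46, giving 10.5%. With 0.9 per two weeks it is 9.4%. With 30% noise the figures are 9.1% and 8.0%.

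**Simulation** (40,000 null trials per row, type I error in %):

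| Scenario | Random intercept | Random slope | Robust SE | Change-score ANOVA |
|---|---|---|---|---|
| Equal correlation, common slope | 4.9 | 4.2 | 5.0 | 4.9 |
| ICC 0.5, SD 0.3 | 5.7 | 4.7 | 5.1 | 5.0 |
| ICC 0.7, SD 0.5 | 8.3 | 4.9 | 5.1 | 5.0 |
| ICC 0.8, SD 0.5 | 9.2 | 4.9 | 5.0 | 4.8 |
| Decay 0.8, 20% noise | 10.6 | 5.0 | 5.1 | 4.9 |
| Decay 0.9, 30% noise | 8.1 | 5.1 | 5.2 | 5.0 |

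Treating week as categorical but keeping only a random intercept does not cure the problem: at f = 50% the simulated error of the week-6 contrast is 9.6%.

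**Two visits.** With complete data at weeks 0 and 6 only, the random-intercept test and the change-score ANOVA coincide. In five fitted data sets the two statistics agreed to four decimals.

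**The case against.** The problem needs two conditions, and the documents establish neither. Several passages favour a two-visit or ANOVA reading. The section headed for primary-endpoint analysis (12.4.1) names the ANOVA. Sections 1 and 1.2.4 define the endpoint as change from baseline to week 6. Section 10 frames its comparison by the same two weeks. Section 10 also applies one model to all secondary outcomes, yet Visual Paired Associates (secondary in Section 1.2.5, exploratory in 1.2.6) is not given at weeks 2 and 4, and the 36-item WHODAS is replaced there by the 12-item form. All of this stands. Against it, the model is written in week number and slope, and the primary task is measured at all four visits. The point is therefore open.

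The plan also does not say that the intercept is the sole random term. Section 12.2 reports power above 80% under other assumptions that it does not describe, so coverage of slope variation cannot be ruled out, but nothing shows it.

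The larger figures ask a lot. An SD of true change of 0.5 exceeds the planned effect of about 0.4, if both are on the baseline SD scale. The 10.5% cell implies a correlation of 0.8 × 0.8³ = 0.41 between weeks 0 and 6. No document favours these cells over the low ones.

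A reader might infer that entering four visits is enough to break the 5% level. It is not: with a common slope and equal correlation the test holds its size (4.9% simulated).

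**Conclusion.** The point holds in doubly conditional form. If weeks 2 and 4 enter, and true slopes differ or correlation falls with time between visits, the random-intercept slope test is anti-conservative. Across the assumed cells with an SD of true change of 0.3 or 0.5, the standard error is 3–15% too small. The effect is small when f is 10% or less. The algebra is firm, but the size rests wholly on assumed variances.

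It would go too far to say that the trial's primary test is invalid as planned, since the ANOVA that the plan also names is unaffected. What the documents do support is that the error rate of the primary test stays undetermined while Sections 10 and 12.2 disagree with Sections 12.1 and 12.4.1 and the visits are not stated. This is worth correcting before analysis.

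**What to change.** Reconcile Sections 10 and 12.2 with Sections 12.1 and 12.4.1: name one primary test and list the visits that enter it.

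- If the ANOVA is primary, or only weeks 0 and 6 enter the mixed model, no further change is needed for the primary test.
- If weeks 2 and 4 enter, add a random slope for week or use robust standard errors. Alternatively, take the week-6 contrast from a model with categorical visit and unstructured covariance, which matches the endpoint in Section 1.2.4.
- In that case, rerun the Section 12.2 power simulation under the chosen model and state its variance inputs.

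The cost is plan wording and analysis code. A random slope adds two variance parameters, which 100 participants with four visits can support, although the slope variance may be estimated at zero. The test is then slightly conservative (4.2% simulated when slopes do not vary). The stated power may fall. As an illustration, at the assumed ICC of 0.774 that yields 88% under the random-intercept model, power with a correct standard error is 80% at f = 20%, 73% at f = 33% and 60% at f = 50%.
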